10.5 Vital Signs

Summary and change from baseline for weight, temperature, heart rate, respiratory rate, and blood pressure will be summarized overall by time point utilizing continuous descriptive statistics.

10.6 Electrocardiograms

PR, QRS, QT, QTc (ie, QTcB and QTcF) and RR intervals and their change from baseline will be summarized for each treatment group by scheduled visit. Patients will be categorized into > 450 , > 480 , and > 500 ms per their maximum post-baseline absolute QTc interval and > 30 and > 60 ms per their maximum change from baseline QTc interval. Additionally, patients will be classified into the following categories: HR ≤ 50 bpm and/or decrease from baseline ≥ 20 bpm; HR ≥ 120 bpm and/or increase from baseline ≥ 20 bpm; PR ≥ 220 ms and/or increase from baseline ≥ 20 ms. The number and percentage of subjects in each category will be summarized for each treatment group.

10.7 Echocardiograms/Multigated Acquisition Scans

Summary and change from baseline for left ventricular ejection fraction (LVEF) will be summarized overall by time point utilizing descriptive statistics. Change from baseline in LVEF will be summarized with number and percentage of patients who have a $>20\%$ absolute decrease from baseline as well.

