4.2. Exclusion Criteria

Patients meeting any of the following criteria will be excluded from the study:

1. Treatment with anticancer therapy, including investigational therapy, or investigational procedures within 14 days or 5 x the half-life (whichever is longer) prior to the first dose of study drug. For prior biological therapies, eg, monoclonal antibodies with a half-life longer than 3 days, the interval must be at least 28 days prior to the first dose of study drug.
2. Prior treatment with DCC-2618
3. Prior or concurrent malignancy whose natural history or treatment have the potential to interfere with the safety or efficacy assessment of DCC-2618. Patients receiving adjuvant cancer treatment are not eligible if those medications are potentially active against GIST or excluded per protocol (refer to [Section 5.12.3](#)).
4. Patient has known active central nervous system metastases.
5. New York Heart Association class II - IV heart disease, active ischemia or any other uncontrolled cardiac condition such as angina pectoris, clinically significant cardiac arrhythmia requiring therapy, uncontrolled hypertension, or congestive heart failure.
6. Arterial thrombotic or embolic events such as cerebrovascular accident (including ischemic attacks) or hemoptysis within 6 months before the first dose of study drug.
7. Venous thrombotic events (eg, deep vein thrombosis) or pulmonary arterial events (eg, pulmonary embolism) within 3 months before the first dose of study drug. Patients with venous thrombotic events ≥ 3 months before the first dose of study drug on stable anticoagulation therapy are eligible.
8. 12-lead ECG demonstrating QT interval corrected by Fridericia's formula (QTcF) >450 ms in males or >470 ms in females at screening or history of long QT interval corrected (QTc) syndrome.
9. Left ventricular ejection fraction (LVEF) $<50\%$ at screening.
10. Use of proton-pump inhibitors within 4 days prior to the first dose of study drug. Other medications that increase gastric pH, ie, histamine H2 receptor antagonists and antacids may be taken provided they are not administered within 2 hours before or after administration of study drug.

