9.2.2.2.2. Safety

Safety endpoints that will be evaluated include TEAEs, AESIs, SAEs, dose reduction or discontinuation of study drug due to toxicity; and changes from baseline in ECOG PS, vital signs, ECG, LVEF, dermatologic examinations, and clinical laboratory parameters.

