9.8.6.4. Echocardiogram/Multigated Acquisition Scans

Assessments will be summarized overall by time point utilizing continuous descriptive statistics. In addition, the change from baseline will be summarized for continuous parameters. For categorical parameters, the n and percentage will be displayed. No formal hypothesis-testing analysis will be performed.

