3.3 Baseline

Unless specified otherwise, baseline measurements will be the most recent (ie, last non-missing) value collected from screening until prior to receiving the first dose of study medication (Cycle 1 Day 1).

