3.6 General Analysis Conventions

Continuous variables will be summarized using descriptive statistics (number of patients, mean, median, standard deviation, minimum, and maximum). Categorical variables will be summarized using frequencies and proportions. Time-to-event data will be summarized via Kaplan-Meier (KM) methodology using the 25th, 50th (median), and 75th percentiles with associated 2-sided 95% confidence intervals.

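### The only categorical LVEF analysis counts falls of more than 20 points, so patients who drop below the 50% screening floor may go uncounted

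*SAP*

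**What the plan says.** Protocol 9.2.2.2.2 lists among the safety endpoints "changes from baseline in ECOG PS, vital signs, ECG, LVEF, dermatologic examinations, and clinical laboratory parameters". LVEF thus enters as a change from baseline. Protocol 4.2 excludes patients with "Left ventricular ejection fraction (LVEF) $<50\%$ at screening", so 50% is the lowest eligible screening value. Table 1 of the protocol schedules an echocardiogram or MUGA scan at screening, Cycle 3 Day 1, every third cycle from Cycle 6, and end of treatment.

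SAP 10.7 plans two things for LVEF:

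- The value and its change from baseline "will be summarized overall by time point utilizing descriptive statistics". SAP 3.6 defines these for continuous variables as "descriptive statistics (number of patients, mean, median, standard deviation, minimum, and maximum".
- The "number and percentage of patients who have a $>20\%$ absolute decrease from baseline".

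Protocol 9.8.6.4 adds only a general sentence, "For categorical parameters, the n and percentage will be displayed", and names no LVEF category or cut-point. SAP 3.4 keeps unscheduled and repeated ECHO/MUGA results out of the by-visit summaries but lets them contribute to worst-case values where applicable. SAP 10.7 defines no worst-value LVEF table. SAP 11 applies the same methods to the open-label period, with baseline redefined in SAP 11.2.

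SAP 10.6, the neighbouring section, treats QTc differently. It classifies patients by maximum post-baseline level (>450, >480, >500 ms) and by maximum change (>30, >60 ms), for each treatment group.

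**The concern.** A count based only on change, with a high cut-off, says nothing about the level a patient reaches. Entry requires at least 50%, so the patients with the least reserve are those just above that floor, and for them a fall of more than 20 points means ending below 30%. The count in SAP 10.7 could be zero while several patients have values in the 30s or 40s. A reader of the LVEF table who wants to know how many patients in each arm went below the level required for entry would not find the answer. LVEF is measured repeatedly and recorded on the eCRF, so the answer is available from data already collected.

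**Working it through.** The documents state no figure for this point that could be reproduced. The main check is threshold arithmetic and needs no distributional assumption.

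**Inputs.** Baseline *B* is the "baseline measurements will be the most recent (ie, last non-missing) value collected from screening until prior to receiving the first dose of study medication" (SAP 3.3). Screening LVEF is at least 50 (Protocol 4.2), so *B* is taken as at least 50. The SAP cut-off is an absolute fall of more than 20, read as percentage points. *V* is a post-baseline value.

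**Rule.** A patient is counted if *B* − *V* > 20, that is, if *V* < *B* − 20. A value is below the floor if *V* < 50. It is below the floor and uncounted if *B* − 20 ≤ *V* < 50. This range is non-empty only when *B* − 20 < 50, that is, when *B* < 70.

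| Baseline (%) | Counted only if below | Uncounted whole-number values under 50 | Uncounted if 20% were a relative fall (counted only if *V* < 0.8*B*) |
|---|---|---|---|
| 50 | 30 | 30–49 | 40–49 |
| 55 | 35 | 35–49 | 44–49 |
| 60 | 40 | 40–49 | 48–49 |
| 65 | 45 | 45–49 | none |
| 69 | 49 | 49 | none |
| 70 | 50 | none | none |
| 75 | 55 | none | none |

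For example, 55 to 36 is a fall of 19 and is not counted, and 50 to 30 is exactly 20 and is not counted. By contrast, 65 to 44 is a fall of 21 and is counted. The last column shows that a relative reading, which the word absolute in the SAP argues against, would narrow the gap but not close it.

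**Illustration of size, on assumed distributions.** The documents give no LVEF distribution or expected effect. Assume a baseline that is normal with mean 62 and SD 6, truncated at 50, and one post-baseline value per patient.

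- Fall with mean 8 and SD 7: 31.8% of patients end below 50%. The SAP rule counts 1 − Φ((20 − 8)/7) = 1 − Φ(1.71) = 4.3%. It catches 13% of those below 50%, 23% of those below 45% and 43% of those below 40%. With the baseline mean moved between 58 and 65, it catches 9% to 17% of those below 50%.
- Fall with mean 5 and SD 6: it catches 3% of those below 50%.
- No mean change, SD 6: 6.6% of patients are still below 50% on a single scan, through variation alone.

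**Check on the remedy.** A worst-value count grows with the number of scans. With no drug effect, the same baseline and independent changes with SD 6, the probability that the worst of *k* scans is below 50% is 1 − E[(1 − Φ((50 − *B*)/6))^*k*]. This gives 6.6% for *k* = 1, 11.7% for *k* = 2 and 19.4% for *k* = 4. The sample-size section assumes median PFS of 4.5 months on DCC-2618 and 1 month on placebo, and the first scheduled post-baseline scan is at Cycle 3 Day 1. The active arm should therefore have more scans per patient.

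**The case against.** The endpoint is change from baseline, and a change-based category fits it. The 50% figure is an eligibility criterion at screening, and the documents set no LVEF limit during treatment. Descriptive statistics include the minimum, so the lowest scheduled value at each visit is displayed. SAP 3.4 names ECHO/MUGA among the results whose unscheduled values can feed worst-case values, and nothing in SAP 10.7 restricts the existing count to scheduled visits. Protocol 7.7.1 requires clinically significant findings to be recorded as adverse events, and these reach the adverse event tables by grade, dose modification and discontinuation. Protocol 9.4 puts all available data in listings.

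All of this stands, and it rules out several stronger readings that a reader might infer:

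- That every patient who falls below 50% is missed. Only falls of 20 points or less are missed.
- That the other LVEF summary is only a mean that hides individual patients. The minimum is shown.
- That unscheduled scans are ignored altogether. They are left out of the by-visit summaries only.
- That cardiac dysfunction would go unreported. The gap is in one table, and other routes exist.
- That 50% is a limit for treated patients. It is not.

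What the objection does not supply is a count. A minimum shows one value per visit, a listing must be tallied by hand, and adverse event reporting depends on the investigator's judgement. None gives the number of patients per arm below 50%.

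**Conclusion.** The gap is real but limited to descriptive safety reporting. For baselines from 50% to below 70%, a patient can go below the screening floor, to as low as 30% from a baseline of 50%, without entering the only categorical LVEF count. This follows from the stated rule and rests only on reading the cut-off as percentage points.

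The number of patients affected is unknown. The simulated shares show the direction under assumed distributions and do not predict this trial. They do not support a claim that the LVEF results will be falsely reassuring.

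No hypothesis test on LVEF is planned, so power, type I error and the primary result are untouched. The level-and-change approach of SAP 10.6 shows that the plan already uses the fuller form for another cardiac measure. The change is a cheap improvement.

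**What to change.** In SAP 10.7, keep the existing count and add beside it, by treatment arm, the number and percentage of patients whose worst post-baseline LVEF is below 50%. State that unscheduled and repeated scans are included, as SAP 3.4 allows. In the same table, give the number of post-baseline scans per patient or the exposure time by arm. An intermediate change category, such as a fall of at least 10 points, is optional; no such cut-point comes from the documents.

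The cost is a row or two in an existing table, from LVEF values already on the eCRF. The downside is a less specific count that takes in ordinary variation near 50% and rises with the number of scans, so it could be inflated in the longer-treated arm. Showing scans or exposure lets the reader judge that. The row is for reporting only and implies no rule for managing patients.

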10.8 Dermatologic assessments

The number and percentage of subjects with new suspicious skin lesions will be summarized overall and by location.

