- A serum pregnancy test will be performed by a central laboratory at screening. Urine pregnancy tests will be performed at all other visits, except Cycle 1 Day 15. Serum pregnancy test may be performed instead of urine, if it is the site’s standard practice and results are received prior to the patient being dosed in the clinic.
- Randomization may occur up to 3 days prior to Cycle 1 Day 1.
- Patients taking anticoagulants will also have a test at Cycle 1 Day 15. Monitoring of coagulation tests must be increased for as long as deemed clinically appropriate following a change in anticoagulant dose during the study.
- Urinalysis testing will be performed at screening, Day 1 of Cycles 2, 3, and 4, and at the EOT Visit. If any result is abnormal, a microscopic analysis will be performed by the central laboratory.
- A full physical examination as defined in Section 6.11.1 will be performed at screening.
- ECOG PS may be performed post dose.
- Vital sign measurements will be collected after the patient has been at rest (seated or supine position) for at least 5 minutes. In addition, weight will be collected at each visit.
- All 12-lead ECGs will be performed after the patient has been at rest (supine or semi-recumbent position) for at least 15 minutes. The rest period begins after the placement of the ECG leads.
- An echocardiogram or MUGA will only be performed at screening, Cycle 3 Day 1, and every third cycle thereafter (ie, Cycle 6, 9, 12, etc), and the EOT Visit, unless deemed clinically appropriate at other times. The same modality (echocardiogram or MUGA) must be used throughout the study. Echocardiogram or MUGA performed as standard of care prior to informed consent may be used as the Screening assessment as long as the echocardiogram or MUGA was performed within 28 days prior to the first dose of study drug.
- All patients will be assessed by a consulting dermatologist for skin lesions, especially for squamous cell carcinoma, actinic keratosis, and keratoacanthomas, within 21 days prior to Cycle 1 Day 1 (baseline). Subsequently, patients will be assessed at Cycle 3 Day 1 and then every third cycle thereafter (ie, Cycle 6, 9, 12, etc.), at the EOT Visit, and as clinically indicated. Dermatologic exam that meets the protocol criteria that was performed as standard of care prior to informed consent may be used

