6.11.6. Dermatologic Examination

All patients will be assessed by a consulting dermatologist for skin lesions, especially for SCC, actinic keratosis, and keratoacanthomas, according to the schedule of assessments in

[Table 1](#) (schedule of assessments) and [Table 2](#) (schedule of assessments for crossover) and as clinically indicated. The examinations must include the entire skin. Dermatologic exam that meets the protocol criteria that was performed as standard of care prior to informed consent may be used as the Screening assessment as long as the exam was performed within 21 days prior to the first dose of study drug. Any new or changing skin lesions noted during the course of treatment must be documented in the patient's source documents and eCRF. In case of suspected SCC or keratoacanthomas, a skin biopsy must be taken for confirmation of diagnosis by a certified pathologist at the clinical site. Samples with confirmed SCC or keratoacanthoma lesions will be sent to a central laboratory for histopathological and/or molecular analysis.

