7. ADVERSE EVENT AND SERIOUS ADVERSE EVENT DOCUMENTATION, SEVERITY GRADING, AND REPORTING

7.1. Adverse Events

An AE is defined as any untoward medical occurrence in a patient administered a pharmaceutical product during the study, which does not necessarily have a causal relationship with the study drug. An AE can be any unfavorable and unintended sign (eg, including an abnormal laboratory finding), symptom, or disease temporally associated with the use of the study drug, whether or not it is considered to be study drug related. This includes any newly occurring event or previous condition that has increased in severity or frequency after the ICF is signed.

Planned hospital admissions or surgical procedures for an illness or disease that existed before the patient was screened in the study and progression of underlying disease are not to be considered AEs unless the condition deteriorated in an unexpected manner during the study (eg, surgery was performed earlier than planned).

Diagnostic and therapeutic non-invasive and invasive procedures, such as surgery, must not be reported as AEs. However, the medical condition for which the procedure was performed must be reported if it meets the definition of an AE.

Elective surgeries or procedures must not be reported as AEs, but must be documented on the appropriate eCRF page.

Each AE must be assessed immediately to determine if it meets the definition of serious (Section 7.8). If a serious adverse event (SAE) occurs, expedited reporting must follow local and international regulations, as appropriate.

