9.8.6.5. Dermatologic assessments

Dermatologic assessments will be summarized by n and percent. No formal hypothesis-testing analysis will be performed.

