Adverse events of special interest (AESI) are serious or nonserious AEs of scientific and medical concern specific to study drug, for which ongoing monitoring and immediate notification by the Investigator to the Sponsor is required. AESIs will be flagged on the eCRF by the investigator. The following AEs are considered AESIs: squamous cell carcinoma of skin (SCC), actinic keratosis, and keratoacanthoma.

The number and percentage of patients by treatment arm with the following categories of TEAEs will be summarized in tables by SOC and PT:

- Any TEAE
- Any TEAE by toxicity grade
- Any TEAE Grade 3/4
- Any drug-related TEAE
- Any treatment-emergent SAE
- Any drug-related treatment-emergent SAE
- Any TEAE leading to dose modification(dose reduction or interruption)
- Any TEAE leading to treatment discontinuation
- Any TEAE leading to study discontinuation
- Any TEAE leading to death
- Any AESI
- Any AESI by toxicity grade
- Any AESI Grade ≥ 3
- Any drug-related AESI

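### SAP 10.8 counts only new suspicious skin lesions, so a baseline lesion that changes on treatment is left out of the dermatologic examination table

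*SAP*

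**What the plan says.** Protocol 6.11.6 has a consulting dermatologist examine the entire skin. On what is recorded it says: "Any new or changing skin lesions noted during the course of treatment must be documented", both in the source documents and in the eCRF. Table 1 of the protocol schedules an examination in the 21 days before Cycle 1 Day 1, then at Cycle 3, every third cycle after that, and at end of treatment.

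Protocol 9.2.2.2.2 lists among the safety endpoints "changes from baseline in ECOG PS, vital signs, ECG, LVEF, dermatologic examinations, and clinical laboratory parameters". The matching methods section, Protocol 9.8.6.5, is brief: "Dermatologic assessments will be summarized by n and percent". It does not limit the summary to new lesions.

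SAP 10.8 consists of one sentence: "The number and percentage of subjects with new suspicious skin lesions will be summarized overall and by location". The SAP defines neither *new* nor *suspicious*. SAP 11 carries the methods of SAP 3.2 to 10.10 into the open-label period, and SAP 11.2 sets a separate baseline for each open-label sub-period.

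On adverse events, Protocol 7.1 includes "any newly occurring event or previous condition that has increased in severity or frequency after the ICF is signed". SAP 10.2 names the events of special interest: "The following AEs are considered AESIs: squamous cell carcinoma of skin (SCC), actinic keratosis, and keratoacanthoma".

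**The concern.** The protocol puts new and changing lesions on the same footing when data are collected, and the endpoint is worded as change from baseline. The SAP keeps only one of the two. A lesion mapped at the baseline examination that grows or alters on treatment is a change from baseline and must be recorded, but in the ordinary sense of the word it is not new.

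Skin is a main focus of this safety plan: all three events of special interest are skin lesions, and the repeated dermatologist visits look for exactly those. The patients affected are those who enter with lesions already present. For them, the only table built from the skin examination would show nothing unless a separate new lesion also appeared. SAP 1 says the SAP sets out where its methods differ from the protocol, yet no difference is stated for this restriction.

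**Working it through.** No power, error-rate or sample-size formula applies. The check sets the passages side by side and then looks for any other route by which a changing lesion could reach a table.

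**Step 1: collection, endpoint and analysis.**

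| Stage | Source | Scope |
|---|---|---|
| Recorded in the eCRF | Protocol 6.11.6 | New or changing lesions |
| Endpoint | Protocol 9.2.2.2.2 | Change from baseline in the examination |
| Protocol analysis | Protocol 9.8.6.5 | Count and percent, no restriction to new |
| SAP analysis | SAP 10.8 | New and suspicious lesions only |

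The SAP narrows the scope twice. *New* removes changes in existing lesions, and *suspicious* removes lesions by a criterion that is not defined.

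**Step 2: can a changing lesion be identified?** Yes. There is a whole-skin examination before the first dose, and changes must be recorded afterwards. The omission comes from the analysis rule, not from a gap in the data the protocol asks for.

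**Step 3: is it tabulated elsewhere from the skin examination?** No. SAP 10.8 is the only SAP section on these assessments.

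**Step 4: is it tabulated elsewhere as an adverse event?** Often, yes.
- A pre-existing condition that worsens after consent is an adverse event (Protocol 7.1).
- A clinically significant assessment must be documented as an adverse event, and a need for further diagnostic testing or intervention is one of the criteria (Protocol 7.7.1). A lesion biopsied under Protocol 6.11.6 for suspected squamous cell carcinoma or keratoacanthoma meets that criterion whether or not it is new.
- TEAEs and AESIs are tabulated by MedDRA system organ class and preferred term (SAP 3.5 and 10.2).

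What remains is a change recorded under Protocol 6.11.6 that the investigator does not report as an adverse event. Protocol 7.7.1 leaves that determination to the investigator. Such a change appears in the listings (Protocol 9.4) but in no planned table.

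**Step 5: the open-label period.** For placebo patients who cross over, SAP 11.2 takes baseline as the last value before the first 150 mg QD dose of DCC-2618. For patients who escalate, it is the last value before the first 150 mg BID dose. A lesion that arose on placebo and changes after crossover is not new against the first of these. A lesion that arose on QD dosing and changes after escalation is not new against the second. The omission therefore repeats in both groups.

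**Step 6: scale.** With the planned arms of 80 and 40, each omitted subject moves a percentage by 1/80 = 1.25 points on DCC-2618 or 1/40 = 2.5 points on placebo. This is only the weight of one subject. The documents give neither how often patients enter with lesions nor how often those lesions change, so no count can be derived.

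**The case against.** The strongest reply is that the adverse event system already captures what matters. A baseline actinic keratosis that worsens is an adverse event by definition and one of the three named events of special interest. A lesion suspicious enough to biopsy must be reported. All available data are listed. On this view SAP 10.8 loses only changes nobody judged clinically significant, in a table with no hypothesis test. A new lesion is also itself a change from baseline, so the table covers the endpoint in part.

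Most of this stands, and it limits the point to one descriptive table. It does not remove the point. The skin examination is a safety endpoint in its own right, alongside adverse events, and a table that depends on investigator reporting is not a substitute for tabulating what the dermatologist recorded.

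A reader might also infer that AESI capture rests only on a tick-box, since "AESIs will be flagged on the eCRF by the investigator". The documents do not support that. The three conditions are named, and AEs are MedDRA-coded and tabulated by preferred term, so a reported event with a missed flag would still appear under its term in the TEAE tables.

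**Conclusion.** The point holds for the dermatologic examination table, in the blinded and open-label periods alike. SAP 10.8 is narrower than the protocol's collection rule and endpoint, and no reason is given. The consequence is modest: an undercount in one descriptive table, mainly of changes not reported as adverse events. No efficacy result or formal test is affected.

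Three stronger readings are tempting and should be resisted:
- *Changing lesions vanish from safety reporting.* They do not. The TEAE tables, AESI tables and listings remain.
- *The number of patients affected can be estimated.* Any figure would need an assumed rate of baseline lesions. Even then it would count patients with a lesion rather than patients whose lesion changes. A patient who also has a new suspicious lesion is already counted.
- *The omission can be judged against the 4% event rate in Protocol 9.1.* That figure is the rate at which 80 patients give about a 95% chance of at least one occurrence (1 − 0.96^80 = 0.962). It says nothing about how many omitted table entries would matter.

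The conclusion assumes that *new* means absent at the relevant baseline examination, and that the eCRF holds what Protocol 6.11.6 requires. The eCRF itself is not among the documents.

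**What to change.** In SAP 10.8, summarize the number and percentage of subjects with new or changing suspicious skin lesions. Show separate rows for new and for changing, by treatment arm and location. Count a subject once in the combined row, and in both separate rows where both apply. State that *new* and *changing* are judged against the baseline of the period analyzed, so that the rule works under SAP 11.2 as well.

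Keep *suspicious*, because counting every benign change could dilute the signal the examination is meant to find, but define it in the SAP. If the restriction to new lesions is intended, say so as a stated difference from the protocol and give the reason.

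The cost is a few lines of SAP text and one slightly wider table from lesion records the protocol already requires in the eCRF. If the eCRF does not distinguish new from changing, the combined row can still be produced. Rows for pathology-confirmed lesions are not proposed, because the documents do not show that pathology results enter the eCRF. A change to how AESIs are identified is not needed for this point.
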